2.4.2.1 ICS in combination with controller medication(s)

ICS in combination with controller medications within 30 days prior to screening of parent study will be summarized for each analysis set ([Section 2](#)) of safety population by the treatment category, and will be sorted by decreasing frequency of standard medication name in the overall category.

The prescription of ICS in combination with controller medication(s) at enrollment of LTS14424 will be summarized by treatment category and overall. Number (%) of patients will be presented by medication names and ICS dose level (medium/high as defined in [Appendix C](#)) according to the classification specified in [\(1\)](#).

2.4.3 Extent of investigational medicinal product exposure and compliance

The extent of IMP exposure and compliance will be assessed and summarized for each analysis set ([Section 2](#)) of safety population by the treatment category.

2.4.3.1 Extent of investigational medicinal product exposure

The extent of IMP exposure will be assessed by the duration of IMP exposure in LTS14424 study.

For each analysis set, duration of IMP exposure is defined as End date of the Treatment Epoch – Start date of the Treatment Epoch +1 as defined in [Table 3](#), regardless of unplanned intermittent discontinuations (see [Section 2.5.2](#) for calculation in case of missing or incomplete data).

Duration of IMP exposure will be summarized descriptively as a quantitative variable (number, mean, SD, median, minimum, and maximum). In addition, duration of treatment exposure will also be summarized categorically by numbers and percentages for each of the following categories and cumulatively according to these categories:

- >0 and \leq 2 weeks
- > 2 and \leq 4 weeks
- > 4 and \leq 8 weeks
- > 8 and \leq 12 weeks
- > 12 and \leq 16 weeks
- ...
- ...
- > 48 and \leq 52 weeks
- > 52 weeks

Additionally, the cumulative duration of treatment exposure, will be provided in patient years by treatment category and overall.

Number and percentage of patients will be summarized by total number of injections they received during the LTS14424 study.

2.4.3.2 Compliance

A given administration will be considered noncompliant if the patient did not take the planned dose of treatment as required by the protocol. No imputation will be made for patients with missing or incomplete data. An administration is considered compliant if an injection is performed, regardless the actual amount of solution injected.

Percentage of compliance for a patient will be defined as the number of administrations that the patient was compliant divided by the total number of administrations that the patient was planned to take during the treatment epoch as defined in [Table 3](#).

Treatment compliance percentages will be summarized descriptively as quantitative variables (number, mean, SD, median, minimum, and maximum). The percentage of patients whose compliance is <80% will be summarized.

Cases of overdose of IMP (defined as at least twice the intended dose during an interval of less than 11 days for 100/200 mg q2w regimen or less than 25 days for 300 mg q4w regimen) will be summarized by numbers and percentages of patients with at least 1 overdose by treatment category. Different overdose intense by dose interval, ie, 1 day, 2 days, etc., will also be summarized. More generally, dosing irregularities will be listed in [Section 2.2.1](#).

2.4.4 Analyses of efficacy endpoints

All analyses will be done descriptively for each analysis set ([Section 2](#)) of safety population by the treatment category. The baseline value for efficacy parameters will be the original baseline from the parent study.

The efficacy analyses will be performed for each analysis set of safety population, and the following populations:

- Exposed patients with type 2 inflammation phenotype at baseline of parent study: either blood eosinophil ≥ 0.15 Giga/L or FeNO ≥ 20 ppb.
- Exposed patients with blood eosinophil ≥ 0.3 Giga/L at baseline of parent study.
- Exposed patients with blood eosinophil ≥ 0.15 Giga/L at baseline of parent study.
- Exposed patients with blood FeNO ≥ 20 ppb at baseline of parent study.

The number of patients with one or more severe exacerbation events (number and qualitative variable: Yes/No), number of severe exacerbation events (qualitative variable: 0, 1, 2, 3, ≥ 4), total number of severe exacerbation events, total patient-years, unadjusted annualized severe exacerbation event rate, and duration (days) of a single severe exacerbation (number, mean, SD,

median, minimum, maximum) during the treatment period will be presented by treatment categories for each analysis set of safety population. Annualized rate will also be analyzed for severe exacerbation with use of SCS for ≥ 3 days only, and those with hospitalization or with emergency room visit only.

For the spirometry efficacy variables listed in [Section 2.1.3](#), descriptive statistics (mean, SD, median, minimum and maximum) will be presented for the parameter and its change from baseline over visits for each analysis set of safety population by the treatment category. In addition, figure of mean change from baseline (with corresponding standard error) will be presented for the continuous efficacy parameter over visits for each analysis set of safety population by the treatment category.

If there were patients who had a long gap between the parent EOT visit and the first dose in LTS14424 study, additional analyses excluding such patients may be conducted for the annualized rate of severe asthma exacerbation and change in % predicted FEV1 on the full analysis set of safety population by the treatment category.

2.4.4.1 Subgroup analyses

Subgroup analyses will be performed for key efficacy variables (severe exacerbation and Percentage (%) predicted FEV1) for each analysis set of safety population:

- ICS dose group: patients on the medium or high ICS dose at the original baseline in the parent study.
- Blood eosinophil (Giga/L) groups at baseline of parent study: ≥ 0.3 , < 0.3 Giga/L; ≥ 0.15 , < 0.15 Giga/L; < 0.15 , ≥ 0.15 - < 0.3 , ≥ 0.3 - < 0.5 , and ≥ 0.5 Giga/L.
- Blood FeNO (ppb) groups at baseline of parent study: < 20 , ≥ 20 - < 35 , and ≥ 35 ppb.
- Baseline age group (6-8, 9-11 years).

2.4.4.2 Multiplicity issues

Not applicable.

2.4.5 Analyses of safety data

The summary of safety results will be presented for each analysis set ([Section 2](#)) of safety population by the treatment category, unless otherwise specified.

General common rules

All safety analyses will be performed on the safety population as defined in [Section 2.3.1](#), unless otherwise specified, using the following common rules:

- Safety data in patients who do not belong to the safety population (eg, exposed but not enrolled) will be listed separately (if applicable).
- The baseline value for safety parameters is defined as the original baseline from the parent study.

- In addition to the baseline values, the pre-dose measurements at Week 0 in LTS14424 will be presented in the by-visit summary/figure for laboratory, vital signs or ECG parameters. The pre-dose measurements at Week 0 are the last available measurements prior to the first IMP dose in LTS14424 study.
- The potentially clinically significant abnormality (PCSA) values are defined as abnormal values considered medically important by the sponsor according to predefined criteria/thresholds based on literature review and defined by the sponsor for clinical laboratory tests, vital signs, and ECG ([Appendix A](#)).
- PCSA criteria will determine which patients had at least 1 PCSA during the analysis set specific treatment-emergent adverse event period as defined in [Section 2](#), taking into account all evaluations performed during the treatment-emergent adverse event period, including non-scheduled or repeated evaluations. The number of all such patients will be the numerator for the on-treatment PCSA percentage.
- The treatment-emergent PCSA denominator for a given parameter will be based on the number of patients assessed for that given parameter in the treatment-emergent adverse event period for each analysis set of safety population by the treatment category.
- For quantitative safety parameters, descriptive statistics will be used to summarize results and change from baseline values for each analysis set of safety population by the treatment category. Summaries will include the endpoint value and/or the worst on-treatment value. The endpoint value is commonly defined as the value collected at the date of last IMP dose +1 dose interval (14 days for last IMP as 100/200 mg q2w and 28 days for last IMP as 300 mg q4w) or the end of treatment visit. If this value is missing, this endpoint value will be the closest value prior to the last administration of IMP + 1 dose interval. The worst value is defined as the nadir and/or the peak post-baseline (up to last administration of IMP + 1 dose interval) according to the direction (minimum or maximum) of the abnormality as defined in the PCSA list.
- All of the values including unscheduled measurements will be assigned to the appropriate safety analysis visit window. The safety analysis visit window is defined in [Section 2.5.3](#).
- The analysis of the safety variables will be essentially descriptive and no systematic testing is planned.

2.4.5.1 Analyses of adverse events

Generalities

The primary endpoint of this study is the number (n) and percentage (%) of patients experiencing any treatment-emergent adverse events (TEAE). Pre-treatment and post-treatment adverse events will be described separately if applicable.

If an adverse event date/time of onset (occurrence, worsening, or becoming serious) is incomplete, an imputation algorithm will be used to classify the adverse event as pre-treatment, treatment-emergent, or post-treatment. The algorithm for imputing date/time of onset will be conservative and will classify an adverse event as treatment-emergent, unless there is definitive information to

determine it is pre-treatment or post-treatment. Details on classification of adverse events with missing or partial onset dates are provided in [Section 2.5.2](#).

Adverse event incidence tables will be presented by system organ class (SOC), high level group term (HLGT), high level term (HLT) and preferred term (PT) sorted in alphabetical order, to summarize the number (n) and percentage (%) of patients experiencing at least one AE in each analysis set of safety population by the treatment category. Multiple occurrences of the same event in the same patient will be counted only once in the tables within a treatment category. The denominator for computation of percentages is number of patients in each analysis set of safety population by the treatment category. In all AE incidence tables, the total patient years (in the unit of 100 patient-years) of each analysis set of safety population by the treatment category will be presented in the corresponding column headers.

The number of events per 100 patient-years (adjusted for the total duration of exposure) of each analysis set of safety population by the treatment category will be presented for each AESI during the corresponding treatment-emergent period.

Sorting within tables ensures the same presentation for the set of all adverse events within the observation period (pre-treatment, treatment-emergent, and post-treatment). For that purpose, the table of all TEAEs presented by SOC and PT sorted by the internationally agreed SOC order and decreasing frequency of PTs within SOCs will define the presentation order for all other tables unless otherwise specified. Sorting will be based on the results for the overall patients across treatment categories, unless otherwise specified.

The following treatment-emergent adverse event summaries for each analysis set of safety population by the treatment category will be generated.

Analysis of all treatment-emergent adverse events

- Overview of treatment-emergent adverse events, summarizing number (%) of patients (including total patient years in column headers) with any:
 - Treatment-emergent adverse event,
 - Treatment-emergent serious adverse event,
 - Treatment-emergent adverse event leading to death,
 - Treatment-emergent adverse event leading to permanent treatment discontinuation.
- All TEAEs by primary SOC, HLT, HLT, and PT, showing number (%) of patients (including total patient years in column headers) with at least 1 treatment-emergent adverse event sorted by the SOC internationally agreed order. The other levels (HLGT, HLT, PT) will be sorted in alphabetical order.
- All TEAEs by primary SOC and PT, showing the number (%) of patients (including total patient years in column headers) with at least 1 treatment-emergent adverse event, will be presented by the internationally agreed SOC order and by decreasing incidence of PTs within each SOC.

- All TEAEs by primary SOC, showing the number (%) of patients (including total patient years in column headers) with at least 1 treatment-emergent adverse event, will be presented by the internationally agreed SOC order.
- All possibly drug-related TEAEs by primary SOC and PT, showing number (%) of patients (including total patient years in column headers) with at least 1 TEAE, will be presented by SOC internationally agreed order and by decreasing incidence of PTs within each SOC.
- All TEAEs by maximal severity, presented by primary SOC and PT, showing the number (%) of patients (including total patient years in column headers) with at least 1 TEAE by severity (ie, mild, moderate, or severe), sorted by the order defined above.
- Number (%) of patients (including total patient years in column headers) experiencing TEAE(s) presented by primary and secondary SOC, HLGT, HLT, and PT sorted by SOC internationally agreed order. The other level (HLGT, HLT, PT) will be presented in an alphabetic order.
- A listing will be provided for all TEAEs.

Analysis of all treatment-emergent serious adverse event(s)

- All treatment-emergent serious adverse events by primary SOC, HLGT, HLT, and PT, showing the number (%) of patients (including total patient years in column headers) with at least 1 treatment-emergent serious adverse event, will be presented by the internationally agreed SOC order. The other levels (HLGT, HLT, PT) will be presented in alphabetical order.
- All treatment-emergent serious adverse events by primary SOC and PT, showing number (%) of patients (including total patient years in column headers) with at least 1 TEAE, will be presented by SOC internationally agreed order and decreasing incidence of PTs within SOC.
- A listing of all serious adverse events will be presented.

Analysis of all treatment-emergent adverse event(s) leading to treatment discontinuation

- All TEAEs leading to treatment discontinuation, by primary SOC, HLGT, HLT, and PT, showing the number (%) of patients (including total patient years in column headers) will be presented by the internationally agreed SOC order. The other levels (HLGT, HLT, PT) will be presented in alphabetical order.
- All TEAEs leading to treatment discontinuation, by primary SOC and PT, showing number (%) of patients (including total patient years in column headers) with at least 1 TEAE, will be presented by SOC internationally agreed order and by decreasing incidence of PTs within each SOC.
- A listing will be provided for all treatment-emergent adverse events leading to treatment discontinuation.

Analysis of adverse events of special interest (AESI) and other selected AE groupings

Summaries of AESI defined by the search criteria:

- All treatment-emergent AESIs and other selected AE groupings identifiable by MedDRA terms, by AESI category and PT, showing the number (%) of patients (including total patient years in column headers), will be presented by decreasing incidence of PT within each AESI category.
- An overview summary within each treatment-emergent AESI and other selected AE groupings will include:
 - Number (%) of patients with any TEAE,
 - Number (%) of patients with any SAE (regardless of treatment-emergent status),
 - Number (%) of patients with any treatment-emergent SAE,
 - Number (%) of patients with any AE leading to death,
 - Number (%) of patients with any TEAE leading to permanent treatment discontinuation,
 - Number (%) of patients with any TEAE by maximum intensity, corrective treatment, and final outcome,
 - Cumulative incidence (K-M estimates) up to specified time points (Week 4, Week 12, Week 24, Week 36, Week 52, Week 64).

Notes for the last bullet: when TEAE start date or worsening date is partially available, the maximum of the earliest possible TEAE start date and the treatment start date will be used. When TEAE start date or worsening date is completely missing, the treatment start date will be used.

- Number of treatment-emergent AESIs and other selected AE groupings per 100 patient-years (total number of events adjusted for the total duration of exposure) will be presented by decreasing incidence of PT within each AESI and other selected AE groupings category.
- The time-to-first AESI event analyzed using Kaplan-Meier (K-M) methods and displayed as K-M plots (cumulative incidence (%)) versus time based on K-M estimates) will be provided to depict the course of onset over time.
- A listing will be provided for AESIs.

Analysis of pre-treatment and post-treatment adverse events

- All pre-treatment AEs by primary SOC and PT, showing the number (%) of patients (including total patient years in column headers) with at least 1 pre-treatment AE, will be presented by the internationally agreed SOC order and by decreasing incidence of PTs within each SOC.
- All pre-treatment SAEs by primary SOC and PT, showing the number (%) of patients (including total patient years in column headers) with at least 1 pre-treatment SAE, will be presented by the internationally agreed SOC order and by decreasing incidence of PTs within each SOC.

- All post-treatment AEs by primary SOC and PT, showing the number (%) of patients (including total patient years in column headers) with at least 1 post-treatment AE, will be presented by the internationally agreed SOC order and by decreasing incidence of PTs within each SOC.
- All post-treatment SAEs by primary SOC and PT, showing the number (%) of patients (including total patient years in column headers) with at least 1 post-treatment SAE, will be presented by the internationally agreed SOC order and by decreasing incidence of PTs within each SOC.

Analysis of adverse events

- All pre-treatment, treatment-emergent, or post-treatment AEs by primary SOC and PT, showing the number (%) of patients (including total patient years in column headers) with at least 1 AE, will be presented by the internationally agreed SOC order and by decreasing incidence of PTs within each SOC.

If there were patients who had a long gap between the parent EOT visit and the first dose in LTS14424 study, additional analyses excluding such patients may be conducted for the key safety variables listed below on the full analysis set of safety population by the treatment category.

- Overview of TEAEs.
- All TEAEs by primary SOC and PT.
- All treatment-emergent serious adverse events by primary SOC and PT.
- All TEAEs leading to treatment discontinuation by primary SOC and PT.
- All treatment-emergent AESIs and other selected AE groupings identifiable by MedDRA terms by AESI category.

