11.4 STATISTICAL METHODS

For each analysis population defined in [Section 11.3](#), the planned analyses will be conducted in the following two analysis sets, respectively.

The full analysis set for each analysis population will include all data observed in the study.

The modified analysis set for each analysis population will censor the data observed on or after the first dose of 300 mg q4w for the patients in this analysis population who were exposed to the 300 mg q4w regimen. Particularly, the patients who will initiate the treatment on 300 mg q4w regimen since Week 0 of LTS14424 study will be excluded from the modified analysis set.

For each analysis set, the planned analyses will be presented by the group of patients according to their actual treatment groups in the parent study EFC14153, specifically, 'Placebo-Dupilumab', 'Dupilumab-Dupilumab', and 'All'.

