1.3 DETERMINATION OF SAMPLE SIZE

The primary objective of the study is to evaluate the long-term safety and tolerability of dupilumab in patients with asthma who participated in a previous dupilumab asthma clinical trial (EFC14153). Hence, the maximal number of patients to participate in this 1-year treatment safety study will be the number corresponding to the total randomized in the previous dupilumab asthma clinical study.

Based on the observed enrollment rate of 87% from parent study to this study, the expected number of sample size for LTS14424 study is approximately 354 patients (that is 87% of 408 patients randomized in the parent study).

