| 2 | 27-Aug-2020 | 
There are a very limited number of patients who are exposed to the new dosage Dupilumab 300 mg q4w. As a consequence, the full analysis set and modified analysis set is highly overlapped. Safety subgroup analyses will be performed on the full analysis set which represents the overall safety evaluation of the study population.
 | "The planned subgroup analyses for key safety endpoints will be performed for each of the full and modified analysis sets of safety population" will be changed to "The planned subgroup analyses for key safety endpoints will be performed for the full analysis set of safety population" |
| 2 | 27-Aug-2020 | Antigen-specific IgE will be assessed along with the total IgE | Add analyses for antigen-specific IgE |

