2 STATISTICAL AND ANALYTICAL PROCEDURES

Generalities

Generally, for each analysis population (Safety, Efficacy, Pharmacokinetics, and Anti-drug antibody) that is defined in [Section 2.3](#), the planned analyses will be conducted in the following two analysis sets:

- The full analysis set: all data observed in the study. The analyses performed on the full analysis set are to evaluate the long-term safety, efficacy, PK and etc. of all the dose regimens that are investigated in the LTS14424 study, that is, dupilumab 100 mg q2w, 300 mg q4w and 200 mg q2w.
- The modified analysis set: 1) For patients never exposed to 300 mg q4w: all observed data will be included 2) For patients that switch from 100 mg q2w to 300mg q4w in LTS14424: data will be included up to the date of first dose of 300 mg q4w with censoring data observed on or after this date 3) For patients that initiate the study on 300 mg q4w (i.e. receive 300 mg q4w at Day 0) no data will be included in this analysis set. The analyses performed on the modified analysis set are to focus on the long-term safety, efficacy, PK and etc. of the same regimens as the parent study, that is, dupilumab 100 mg q2w and 200 mg q2w.

Observation period

The observation period will be divided into 4 epochs which are defined in [Table 3](#) according to the two analysis sets.

The treatment-emergent adverse event period will include both treatment and residual treatment epochs that are defined in [Table 3](#). The post-treatment adverse event period will be the post-treatment epoch.

The pre-treatment adverse event period will be from the start of AE reporting in LTS14424 up to the first dose of IMP in LTS14424. For all the periods aforementioned, both date and time shall be used in the determination of the periods, as long as they will be available.

Table 3 - Study epoch definition by analysis set

| Analysis Set | Epoch | Applicable Patients | Epoch Start | Epoch End |
|-------------------|--------------------|---------------------------------------------------|-----------------------------------|-----------------------------------------------|
| Full analysis set | Screening | All | – | The day before the date of first IMP |
| | Treatment | Patients with last IMP on 100mg/200mg q2w regimen | Date of the first IMP in LTS14424 | Date of last IMP +14 days |
| | | Patients with last IMP on 300 mg q4w regimen | Date of the first IMP in LTS14424 | Date of last IMP +28 days |

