| | Residual treatment | Patients with last IMP on 100mg/200mg q2w regimen | Date of last IMP +15 days | Date of last IMP +14 days +12 weeks (84 days) |

| Analysis Set | Epoch | Applicable Patients | Epoch Start | Epoch End |
|------------------------------------------------------------------------------------------------------------------------------|--------------------|-------------------------------------------------------------|----------------------------------------------|-----------------------------------------------|
| | | Patients with last IMP on 300 mg q4w regimen | Date of last IMP +29 days | Date of last IMP +28 days +12 weeks (84 days) |
| | Post-treatment | All | Residual treatment Epoch End date +1 day | Open ended |
| Modified analysis set (not applicable to patients who initiate the treatment on 300 mg q4w regimen since Week 0 of LTS14424) | Screening | All | -- | The day before the date of first IMP |
| | Treatment | Patients on 100 mg/200 mg q2w regimen only | Date of the first IMP in LTS14424 | Date of last IMP +14 days |
| | | Patients who switched regimen from 100 mg q2w to 300 mg q4w | Date of the first IMP in LTS14424 | The date before the first dose of 300 mg q4w |
| | Residual treatment | Patients on 100 mg/200 mg q2w regimen only | Date of last IMP +15 days | Date of last IMP +14 days +12 weeks (84 days) |
| | | Patients who switched regimen from 100 mg q2w to 300 mg q4w | N/A | N/A |
| | Post-treatment | Patients on 100 mg/200 mg q2w regimen only | Residual treatment Epoch End date + 1 day | Open ended |
| | | Patients ever switch regimen from 100 mg q2w to 300 mg q4w | N/A | N/A |

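### In the modified analysis set, children switched to 300 mg q4w count in full in the any-TEAE denominator although their TEAE period stops at the switch, so the crude percentage can understate full-window risk on the q2w regimens

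*SAP*

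**What the plan says.** The primary endpoint of the main study is the number and percentage of patients with any TEAE (Protocol 9.1; SAP 2.4.5.1). Protocol 11.4 says that "the planned analyses will be conducted in the following two analysis sets, respectively", meaning the full set and the modified set. SAP 2.4.5.1 generates the TEAE tables for both.

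For the modified set:

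- **Purpose.** SAP Section 2 says its analyses "are to focus on the long-term safety, efficacy, PK and etc. of the same regimens as the parent study", that is, 100 mg q2w and 200 mg q2w.
- **Who is in it.** Children who start LTS14424 on 300 mg q4w are removed. Children who switch from 100 mg q2w stay in.
- **Follow-up of switchers.** In SAP Table 3 their treatment epoch ends at "The date before the first dose of 300 mg q4w", and the residual epoch is marked not applicable. Protocol 11.4.3.1 has the same rule.
- **Follow-up of children never on 300 mg q4w.** The TEAE period runs to the last dose plus 14 weeks.
- **Denominator.** "The denominator for computation of percentages is number of patients in each analysis set of safety population by the treatment category" (SAP 2.4.5.1).

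Total patient-years appear in the column headers of the incidence tables. Events per 100 patient-years and Kaplan-Meier cumulative incidence are planned for AESIs and other selected AE groupings, but not for any TEAE, SAE or TEAE leading to discontinuation.

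**The concern.** A switcher with no TEAE before the switch is tabulated as TEAE-free on the same footing as a child observed for about 64 weeks. The shortened window can remove events from the numerator, but it never removes the child from the denominator. The resulting percentage is nevertheless the one offered as the long-term safety of the parent-study regimens.

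Elsewhere the plan does respect the shorter window. Exacerbation rates in the modified set use a censored observation period and patient-years (Protocol 11.4.2; SAP 2.1.3.1). PCSA percentages count only patients assessed in the TEAE period (SAP 2.4.5). AESIs get rates and Kaplan-Meier estimates. The any-TEAE percentage gets none of these.

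**Working it through.** **The plan's own figure.** SAP 1.3 derives the sample size as follows: "Based on the observed enrollment rate of 87% from parent study to this study". The arithmetic is 0.87 × 408 = 354.96, against the stated figure of about 354, so it reproduces. There is no alpha or power to check, because "The analysis of the safety variables will be essentially descriptive and no systematic testing is planned".

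**Inputs**

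- Full q2w window: last dose at Week 50 (Protocol 6.2.1) plus 14 weeks (Protocol 11.4.3.1), giving T = 64 weeks.
- Possible switch weeks w within the modified set: 4, 8, ..., 44 (Protocol 8.1.1). A Week 0 start on 300 mg means removal from the set.
- Share of switchers f: not given. SAP 1.6 says that very few patients were exposed to 300 mg q4w and that the two sets overlap heavily. Assumed 2% to 5%.
- Full-window risk p: not given for this trial. The placeholder is 79.1%, the pooled dupilumab figure from the adult Phase 2b study in Protocol 4.2; its observation period is not stated there.
- Switch times: assumed evenly spread over the listed weeks.

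**Direction.** Let m be the average risk of a TEAE before the switch. Then

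crude modified-set % = (1 − f) × p + f × m, and shortfall = f × (p − m).

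A shorter window cannot contain more first events than a longer one, so m ≤ p and the shortfall is zero or positive.

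**Size**

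- Constant hazard: λ = −ln(1 − 0.791)/64 = 0.0245 per week. m is the mean of 1 − exp(−λw), which is 41.7%.
- Front-loaded hazard (Weibull, shape 0.6): m is the mean of 1 − exp{ln(1 − 0.791) × (w/64)^0.6}, which is 54.6%.

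| f | Constant hazard | Front-loaded hazard |
|---|---|---|
| 2% | 0.02 × (79.1 − 41.7) = 0.75 points | 0.02 × (79.1 − 54.6) = 0.49 points |
| 5% | 0.05 × 37.4 = 1.87 points | 0.05 × 24.5 = 1.2 points |

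Under constant hazard the modified-set percentage would read 78.4% or 77.2% instead of 79.1%.

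**Sensitivity**

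- With p from 50% to 85%, the shortfall is 0.4 to 0.75 points at f = 2% and 1.0 to 1.9 points at f = 5%, across both hazard shapes.
- Timing matters more. At p = 79.1% and constant hazard, all switches at Week 4 would give 1.4 points (f = 2%) or 3.5 points (f = 5%). All switches at Week 44 would give 0.3 or 0.7 points.

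**Does the remedy work?** In a simulation of 200,000 patients, with constant hazard and f set to 10% only to make the effect visible, the crude percentage was 75.4%. Kaplan-Meier with censoring at the switch gave 79.2%, against a true 79.1%. The simulation assumes that switching is independent of TEAE risk.

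**The case against.** **A reader might infer that the primary result is undefined**, since two sets times three columns give six percentages and no sentence names one. The documents do not support that as a serious defect. Protocol 9.1 defines the endpoint over the total study periods, and Protocol 11.4.3.1.1 uses the whole safety population as denominator. Only the full set fits both. SAP 1.6 adds: "Safety subgroup analyses will be performed on the full analysis set which represents the overall safety evaluation of the study population". That sentence explains where subgroup analyses are run, so it does not formally assign the endpoint, but it points the same way. Both sets are prespecified, both must be tabulated and nothing is tested, so neither result can be hidden. What remains is a wording clarification.

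**A reader might also infer that the modified-set percentage must fall below the full-set one.** It need not, because the modified set also drops the children who started on 300 mg q4w. The shortfall is relative to full-window risk on the q2w regimens, not to the full set.

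**The unequal follow-up is partly disclosed.** SAP 2.4.3.1 requires exposure duration, duration bands and cumulative patient-years for each set. This stands as disclosure, but it does not correct the percentage. If the header patient-years follow that exposure definition, they also omit the 12-week residual period in which TEAEs of children never on 300 mg q4w still count.

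**Crude incidence always mixes follow-up lengths**, including those of early discontinuers. That is true. Here, however, later data exist and are set aside by rule.

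**The size rests on assumptions.** This stands. Shares of 10% or 20% switchers would give larger shortfalls but fit poorly with the SAP's own description of exposure.

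**Conclusion.** The point holds for the modified set. Followed as written, the plan reports an any-TEAE percentage that is at or below the full-window risk on the q2w regimens. The likely size is small, about 0.5 to 1.9 points. That range assumes 2% to 5% switchers, a 79.1% placeholder risk and evenly spread switch times; concentrated early switching would enlarge it. It is zero if every switcher had a TEAE before switching. The full-set percentage is untouched by this rule, so the main safety conclusion does not depend on it. The case for acting is that the direction is built into the rule and the remedy reuses methods already planned.

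**What to change.** In SAP 2.4.5.1, for the modified set:

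1. For any TEAE, SAE and TEAE leading to discontinuation, add one of two measures. Either use Kaplan-Meier cumulative incidence at the time points already set for AESIs, with switchers censored the day before the first 300 mg dose. Or use patients with a first event per 100 patient-years at risk, with time at risk counted over each child's TEAE period and not over the treatment epoch alone.
2. Report the number of switchers.
3. Footnote the crude percentages as based on unequal follow-up.

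As clarifications only:

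- State that the full set, All column, gives the primary-endpoint result and that the modified set is supportive.
- Align the denominator wording in Protocol 11.4.3.1.1 (all patients in the safety population) with SAP 2.4.5.1 (patients in the analysis set). Applied literally to the modified set, the protocol wording would count Week 0 starters who contribute no data.

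The cost is a few sentences and a modest amount of extra output, with no new data. The limitation is that Kaplan-Meier treats the switch as independent of TEAE risk. Only children of 30 kg or less can switch, so censoring is tied to weight; the table should say so.
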